More than 80% of older adults have hypertension, with higher prevalence of high systolic blood pressure (SBP) putting them at high risk for cardiovascular (CV) disease and death. Because drug therapy that lowers SBP is associated with side effects such as hypotension, syncope, and kidney dysfunction, there is a great need for effective lifestyle SBP-lowering interventions for the older population that can replace drug therapy. While aerobic exercise is a recommended lifestyle intervention for controlling SBP and preventing CV disease naturally, in older adults it has been shown to be less effective in vascular-tissue remodeling because of arterial stiffness, resulting in less efficient SBP control. Reduced bioavailability of nicotinamide adenine dinucleotide (NAD+), a cofactor for the deacetylase sirtuin1 (SIRT1), may contribute to age-related vascular dysfunction via oxidative stress and reduced nitric oxide (NO). Exercise-induced overexpression of NAD+-dependent SIRT1 improves the bioavailability of NO. Preclinical evidence suggests that poor vascular-function improvement in response to exercise in older mice is caused by insufficient NAD+ levels to stimulate SIRT1 activity. Importantly, replenishment of NAD+ levels induced vascular remodeling, improved vascular function, and reduced SBP in mice. An objective of this study, therefore, is to test a combination of aerobic exercise and nicotinamide riboside, a compound that replenishes NAD+ levels, to optimize exercise's SBP-lowering effect in hypertensive older adults. Initial human clinical trials demonstrated that nicotinamide riboside supplementation (1,000 mg/day) was safe and showed a higher potential to reduce SBP and arterial stiffness in participants with elevated SBP. As we have preclinical evidence that combining NAD+ replenishment with exercise is an ideal strategy for improving vascular function, our central hypothesis is that the intervention of aerobic-exercise training combined with nicotinamide riboside supplementation will reduce SBP in hypertensive older adults more effectively than will exercise alone. We will enroll 54 participants \geq 55 years and older into either: (1) 1,000 mg/day of nicotinamide riboside plus 3 days/week of supervised, center-based walking exercise (n=18), or (2) the same exercise program combined with placebo (n=18), or (3) 1,000 mg/day of nicotinamide riboside alone (n=18). All participants will undergo daytime continuous SBP at baseline, 3 weeks, and 6 weeks, and arterial-stiffness measurements by pulse-wave velocity at baseline and at 6 weeks. Elevated SBP will be determined as daytime average equal to or above 130 mmHg, measured by the 24-hour blood-pressure device. To our knowledge, this study will be the first attempt to enhance exercise therapy with nicotinamide riboside in hypertensive older adults. We believe that nicotinamide riboside is "the missing piece of the puzzle" in improving vascular remodeling and SBP management in older adults. Preliminary evidence from this pilot study may support a full-scale Phase III clinical trial in hypertensive older adults. The ultimate goal of this line of research is to find adjuvant strategies to improve the exercise's SBP-lowering effects in older adults.

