The objective of this study is to conduct a pilot study to refine and finalize elements critical to conducting a future, definitive randomized, controlled trial (RCT). We propose to recruit 54 persons aged ≥ 55 years with SBP ≥ 130 mmHg and < 160 mmHg for 6 weeks. Participants will be randomly assigned to receive either (1) 1,000 mg/day of NR plus 3 days/week of supervised, center-based walking exercise, or (2) the same exercise program combined with placebo, or (3) 1,000 mg/day of NR alone. Inclusion of all treatment groups will be important for detecting the potential benefit of NREx. High SBP will be determined at screening as daytime average above or equal 130 mmHg and below 160 mmHg, measured by the 24-hour BP device. All enrolled participants will undergo daytime continuous SBP measurements at baseline, 3 weeks, and 6 weeks, and arterial-stiffness measurements by pulse-wave velocity (PWV) at baseline and 6 weeks. This study will enable us to address the following aims, all of which are of critical importance for designing a full-scale trial.

Aim 1. To obtain critical data necessary to project the sample size needed for a full-scale trial using the change in SBP, as the primary outcome and;

Aim 2. Using the change in arterial stiffness, as the secondary outcome.

6. Research Plan:

We propose to conduct a randomized, controlled pilot trial to test if nicotinamide riboside improves an effect of aerobic exercise training on cardiovascular function among hypertensive older adults. Following study entry, participants (N = 54) will be randomly assigned to either NREx, NR or PLEx groups for 6 weeks. Exercise groups will be involved in three center-based walking training sessions per week. We anticipate that up to an additional 20 individuals enrolled may discontinue participation in the project prior to completion, and that we may have to screen up to 250 additional individuals to reach our recruitment goal of 54 subjects.

6.1 Participants: Eligible participants will be males or females ≥ 55 years of age with daytime average SBP ≥ 130 mmHg and < 160 mmHg.

Table 3.1.1. Inclusion and exclusion criteria.

Inclusion Criteria

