*The physical exam/nursing assessment can be completed at either Screening Visit 1 or at the Baseline Visit as long as it is prior to randomization.

Adherence to interventions. To enhance adherence to the study interventions (compliance), we will utilize empirically-supported techniques which we have successfully utilized in prior studies. Our first step will be to fully inform participants of study requirements before randomization and enroll only those persons who are willing to complete all study procedures. Undoubtedly, however, issues arise after randomization with the potential to limit compliance. Common causes of poor compliance include vacations, spouse care, fatigue, and fluctuations in motivation, perceived lack of benefit, physical discomfort, and adverse health experiences. First, we have designed the trial, including the inclusion/exclusion criteria and physician monitoring, to limit the likelihood of experiencing adverse health events in response to the interventions. In addition, care will be taken by the interventionists to promote the safe engagement in the exercise intervention. For other issues of non-compliance, we will approach this potential problem using a social problem solving model ("toolbox") approach in dealing with individual adherence problems.²⁸ This approach assumes that the process of changing behavior is a collaborative effort between the participant and the interventionists, and that behavior change can be readily undertaken during the regular weekly contacts that intervention staff will initiate throughout the course of the intervention, as well as during face-to-face visits. Our team has successfully applied this type of problem-solving approach in promoting adherence to behavioral interventions in prior studies.

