Arterial Stiffness	Aortic pulse-wave velocity (PWV), commonly measured as carotid to femoral PWV (cfPWV), is considered to be the gold standard method of assessing arterial stiffness in humans. cfPWV will be measured using the SphygmoCor XCEL system (AtCor Medical, New South Wales, Australia). Briefly, cfPWV will be determined by recording pressure pulse waves at the carotid and femoral arteries using a high-fidelity micromanometer (Millar Instruments, Houston, TX) and calculating the distance between the recording sites divided by the time delay between the carotid and the femoral pulse waves [13].

6.10 Sample size justification. This pilot study will help generate precise estimates of effect variance in the population in which a subsequent larger-scale study will be conducted. Published recommendations for the design of pilot studies indicate that a sample of 18 participants per randomized arm is typically sufficient to estimate a parameter for a future trial [14-16]. The enrollment sample of 54 (n=18 x 3 arms) participants is intended to provide preliminary data necessary to indicate feasibility of a larger trial and to provide descriptive estimates of effects. Based on our experience from the past and current clinical trials conducted at our institute, we do not expect an attrition higher than 15%, therefore, we increased a group size to n=18, which will give us sufficient sample sizes for the pilot purposes after drop-out (n=15 x 3 groups). The data will also provide for nominal estimation (using a 95% CI) of mean changes in dependent variables within each arm. By assuming the mean decrease in SBP after a 6-week of intervention to be 20 mmHg, 10 mmHg and 15 mmHg in the three groups of NREx, PLEx and NR, respectively, and the standard deviation of the SBP decreases to be 10 [16], the sample size of 15 participants for each group can guarantee a power of 85% to detect the difference between the NREx and PLEx groups and a power of about 80% to detect the differences among the three groups. We expect that the differences of the arterial-stiffness measurements among the three groups are larger than those of SBP. Thus, the power numbers for that measure will be larger as well.

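### Do the additional 20 people expected to discontinue (section 6) conflict with the 15% attrition already built into the 54 (section 6.10)?

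*Combined protocol and SAP*

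**What the plan says.** Section 6 (Research Plan) gives the number randomized: "Following study entry, participants (N = 54) will be randomly assigned to either NREx, NR or PLEx groups for 6 weeks". It then makes two allowances. The first is for discontinuation: "We anticipate that up to an additional 20 individuals enrolled may discontinue participation in the project prior to completion". The second is for screening: "we may have to screen up to 250 additional individuals to reach our recruitment goal of 54 subjects".

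Section 6.10 (Sample size justification) treats 54 as the number before drop-out: "The enrollment sample of 54 (n=18 x 3 arms) participants is intended to provide preliminary data". On losses it says "we do not expect an attrition higher than 15%, therefore, we increased a group size to n=18", and it gives the result as a size "which will give us sufficient sample sizes for the pilot purposes after drop-out (n=15 x 3 groups").

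The opening summary says "We will enroll 54 participants" and divides them 18 to each of three arms. Section 6.3 places informed consent at the start of the screening visit, before eligibility is checked. Table 1 puts the screening visit at week -2 and the baseline visit, where randomization takes place, at week 0. Section 10 makes the primary analysis intent-to-treat, with changes from baseline as the responses. No section defines *enrolled*, says when the 20 leave, or says whether anyone who drops out is replaced.

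**The concern.** Section 6.10 has already paid for attrition inside the 54. Section 6 then mentions up to 20 further enrolled people who do not finish, and counts them apart from the 250 additional people screened. If these 20 are randomized participants who drop out and are replaced, attrition is allowed for twice and at different rates. The number randomized could then exceed 54 by up to 20.

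This would affect the analysis set. Pulse-wave velocity is measured only at baseline and week 6, so anyone who leaves before week 6 contributes no change in arterial stiffness. Anyone who leaves before week 3 contributes no change in SBP. A larger group of replaced dropouts would mean a larger share of randomized people without a response. There would also be a temptation to analyse only those who finished.

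**Working it through.** **Inputs.** From section 6.10: 15 completers per arm, attrition at most 15%, three arms, 18 per arm. From section 6: 54 randomized and up to 20 additional discontinuing.

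**Step 1: reproduce section 6.10.**
- Per arm: 15 / (1 − 0.15) = 17.65, rounded up to 18.
- Total: 18 × 3 = 54.
- Expected loss at 15%: 54 × 0.15 = 8.1 people, leaving 54 × 0.85 = 45.9. The plan states 15 × 3 = 45.

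The figure of 54 is correct on its own inputs.

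**Step 2: try each reading of the 20.**

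| Reading | Randomized | Lost after randomization | Completers |
|---|---|---|---|
| (a) The 20 leave between consent and randomization | 54 | 8.1 (15%) | about 46; 45 planned |
| (b) The 20 are randomized dropouts who are replaced | 54 + 20 = 74 | 20/74 = 27.0% | 54, or 18 per arm |
| (c) The 20 come out of the 54 | 54 | 20/54 = 37.0% | 34, or about 11 per arm |

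**Step 3: compare each reading with the text.**
- Reading (c) does not fit a sentence that calls the 20 additional.
- Reading (b) needs a replacement rule that appears nowhere. It also puts 74 people through randomization, in a paragraph that says 54 are randomized.
- Reading (a) agrees with the 54 in section 6, with 18 per arm in the opening summary and section 6.10, and with the visit schedule. Consent comes first and randomization a nominal two weeks later, after screening procedures and a full baseline visit. There is room for people to sign up and then withdraw without being allocated.

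**Step 4: is 20 out of line with 15%?** Under (b), finishing with 54 at 15% attrition would need 54 / 0.85 = 63.5, so 64 randomized and 10 extra. But section 6 gives 20 as an upper limit on what may happen, and 10 lies inside it. A recruitment allowance and an expected attrition rate conflict only if both are ceilings on loss after randomization, which the text does not say.

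**Step 5: what happens to the analysis?** Under (a) nothing changes. Under (b) completers number 18 per arm against the 15 on which the power statement rests, so information is gained. In either case intent-to-treat keeps everyone randomized in the group to which they were assigned.

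**The case for a change.** The best case for acting rests on the plan's own vocabulary. The opening summary enrolls people into arms, section 5 uses the word for people measured through week 6, and section 6.10 calls 18 × 3 the enrollment sample. Leaving before completion also sounds more like abandoning a course already begun than failing to start one, and screening losses are counted separately. On that usage the 20 would be randomized participants. A pilot meant to show the feasibility of a larger trial ought to be clear about the attrition it expects.

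Part of this stands. The word is used loosely, the timing of the 20 is not given, and reading (b) cannot be excluded on language alone. But the usage is not uniform. The paragraph on adherence describes a first step to "fully inform participants of study requirements before randomization and enroll only those persons who are willing to complete all study procedures", and only afterwards turns to problems arising after randomization. That fits enrollment before allocation at least as well.

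The point about missing responses is real, but it does not depend on the 20. Section 10 does not say how participants without any post-baseline value are handled, and that silence matters equally if 54 are randomized and about 8 are lost. It is a separate question and adds no weight to this one.

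**Conclusion.** No inconsistency is shown and no change follows. The number randomized is 54 wherever the plan states it, section 6.10 reproduces exactly, and the two sections are compatible when the 20 are people who withdraw before allocation. The figures of 74 randomized and 27% attrition follow only from a replacement policy that the plan does not contain.

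What remains is an undefined word and an unstated timing. A coordinator following the plan would randomize 54 people, 18 per arm, and an analyst would keep all of them under intent-to-treat. That gives sound results with no number altered.

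The conclusion assumes that the explicit 54 governs over the looser sentence after it, and that the 20 are additional to the 54, as written. If the sponsor did intend replacement, completers would rise to 18 per arm and the power basis of 15 per arm would still be met. Only reading (c), with about 11 completers per arm, would hurt, and the word *additional* argues against it.

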
4. Background:

More than 80% of older adults are diagnosed with hypertension and thus are at high risk of atherosclerosis, cardiovascular (CV) events, and death [1]. Systolic blood pressure (SBP) is the most common form of hypertension and is considered more important than diastolic blood pressure (BP) as an independent CV disease risk factor [2]. SBP equal to or above 130 mmHg needs treatment, as even 10-mmHg elevation doubles the risk of a heart attack [3]. Because successful reduction of SBP with medication is often accompanied by side effects such as hypotension, syncope and kidney dysfunction [2], there is a great need for effective lifestyle SBP-lowering interventions in the older population.

The major contributors to high SBP are decline in endothelial function, decline in capillary vessel density, and arterial stiffening, which are profound changes in vascular aging [4, 5]. Reduced bioavailability of nicotinamide adenine dinucleotide (NAD+), a cofactor for the deacetylase sirtuin1 (SIRT1), may contribute to age-related vascular dysfunction via oxidative stress and reduced nitric oxide (NO) [6]. Endothelial dysfunction reduces bioavailability of NO, which increases arterial stiffness and elevates SBP [6]. Interventions that elevate NAD+ levels and increase SIRT1 activity may be critical for improving therapies that target endothelial dysfunction and arterial stiffness to manage SBP and prevent CV disease in older adults.

While aerobic exercise is recommended for SBP control and CV disease prevention [7], it has been shown to be less effective in lowering SBP in older adults because of arterial stiffness [8]. Preclinical evidence suggests that age-related lower vascular function improvement in response to exercise may be caused by insufficient levels of NAD+ to stimulate SIRT1 activity and induce vascular remodeling for SBP reduction [9]. In particular, preclinical evidence showed that in old mice with replenished NAD+ by administration of nicotinamide mononucleotide (NMN), exercise was more effective in stimulating SIRT1 activity and restoring endothelial function and capillary density, compared to mice with lower NAD+ levels [9]. Such findings suggest that replenishment of NAD+ levels with metabolites (e.g., nicotinamide riboside (NR) or NMN) may be the key to enhancing vascular function in response to aerobic-exercise training and, thus, reducing SBP in older adults more effectively.

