
• Age 55 years and older• Daytime average of systolic blood pressure of ≥ 130 mmHg and < 160 mmHg.• Sedentary lifestyle, defined as < 150 min/wk of moderate physical activity as assessed by the CHAMPS questionnaire.• Willingness to be randomized to either treatment group• Willingness to participate in all study procedures
Exclusion criteria

• Failure to provide informed consent.• Pregnant• Change in blood pressure therapy (type or dose) within the last 3 months- Temporary Exclusion• Daytime average of systolic blood pressure ≥ 160 mmHg.• Regular consumption of nicotinamide riboside supplement• Current involvement in supervised rehabilitation program

- Absolute contraindication(s) to exercise training according to American College of Sports Medicine guidelines [11]
- Daytime average of systolic blood pressure below 130mm Hg or Diastolic BP \geq 100mm Hg.
- Peripheral vascular disease; peripheral neuropathy; retinopathy
- Severe cardiac disease, including NYHA Class III or IV congestive heart failure, clinically significant aortic stenosis, history of cardiac arrest, use of a cardiac defibrillator, or uncontrolled angina;
- Myocardial infarction or stroke within past year
- Significant cognitive impairment, including known dementia diagnosis or a Mini-Mental State Examination exam score < 24
- Progressive, degenerative neurologic disease, e.g., Parkinson's Disease, multiple sclerosis;
- Severe rheumatologic or orthopedic diseases, e.g., awaiting joint replacement, active inflammatory disease;
- Severe pulmonary disease, requiring steroid therapy or the use of supplemental oxygen;
- Hip fracture, hip or knee replacement, or spinal surgery within past 4 months;
- Other significant co-morbid conditions that would impair ability to participate in the exercise-based intervention
- Simultaneous participation in another intervention trial

6.2 Recruitment: Participant recruitment will be coordinated in conjunction with the *OA/C Clinical Research Core*, led by co-investigator [name]. We will develop a targeted recruitment approach based on previous experiences utilizing methods of recruitment that include direct mailings, newspaper classified and print ads, community luncheons and health fairs, as well as clinic referrals. We have been extremely successful in implementing this approach in past studies

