6.3 Screening and Study Entry: Participants deemed eligible based on an initial phone screening by our front desk manager, will be encouraged to consult with their physician and invited to an in-person screening visit. During this visit, potential participants will first be asked to give their informed consent and then will be screened for study entry criteria. Initial screening procedures will include a review of their medical history, medication use, a physical exam or nursing assessment, physical activity levels, cognitive function (assessed by the Mini-Mental State Exam), measurement of vital signs, height and weight, BMI (calculated in database only), collection of demographics information, single 24-hour ambulatory SBP monitoring (daytime average SBP \geq 130 mmHg and <160 mmHg – qualifying criterion), and urine collection for a pregnancy test. If all study entry criteria are met, participants will be scheduled to return to the clinic for baseline assessments. In addition, the study participants will be asked to sign Medical Records Release Authorization if they qualify. This Authorization will be used exclusively to obtain medical records to acquire facts, details, and outcomes of Serious Adverse Events that occurred during the study and have to be reported to the sponsor and/or IRB.

6.4 Baseline Assessment and Randomization: If all study entry criteria are met, participants will be scheduled to return to the clinic for baseline assessments prior to randomization. Participants who have not yet had a physical evaluation or nursing assessment will complete this before undergoing physical tests. Participants will be asked to provide a fasting blood sample for evaluation of clinical safety lab values. We will also collect urine samples (first sample collected between 8 am to 11 am and another sample collected between 5 pm to 8 pm) at this visit, which will be slow frozen in a -80 freezer and analyzed after data collection is complete. The first sample will be collected when the participant comes in the morning to participate in the in-person visit. Then, the study coordinator will provide the urine sample collection cup for the participant to bring back home to collect the second urine sample. The study coordinators can help transport the second urine sample or, if the participant prefer, the participant could bring the urine sample back to the study coordinator. In addition, vital signs and weight

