will be measured, as well as exercise capacity with the 6-Minute Walk Test and self-assessed functionality with the Late Life Function and Disability Instrument (LLFDI). Participants will also be given the 24-h BP device to complete the 24-hour ambulatory recording and will have their arterial stiffness assessed. We will also collect adverse events and update medication changes. Finally, the study coordinator will provide participants with a supplement intake form to take home to record when the supplement is taken. Staff members will then discuss randomization procedures with participants. The participants will receive a return envelope/box to return the ambulatory BP device after the 24-hour recording.

6.5 Exercise Intervention: After random assignment to either the NREx or the PLEx groups, participants will engage in a three-days a week, center-based walking exercise intervention for 6 weeks. Following a brief warm-up, participants will be instructed to walk for 30 minutes at a 5-6 on the CR10 scale with encouragement for 10 minutes to be vigorous (7-8 on CR10 scale). Sessions will also include balance training to promote cool-down. Participants will be introduced to exercises in such a way that they begin with lighter intensity and gradually increase. The progressive nature of the intervention is designed to minimize discomfort and prevent injury. Blood pressure will be measured prior to each exercise session; the participant will not complete the session that day if he or she has an in-person SBP >200 mmHg or DBP >110 mmHg (AHA guidelines for exercise contraindication) measured at the exercise center.

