6.6. Supplementation: Participants will be randomly assigned to receive, in a double-blind fashion, either 1,000 mg/day of encapsulated NR (Niagen®) or placebo. The company ChromaDex (Irvine, CA) will provide both the NR and placebo capsules for the proposed study. Placebo capsules will be identical to those including NR. As noted above, a 6-week NR study of Martens et al. demonstrated that NR supplementation at a dose of 1,000 mg/day was safe in rather healthy middle-aged and older adults. Subjects will ingest NR (NIAGEN®; 500 mg, twice per day; ChromaDex, Inc.) or alike looking placebo capsules [10]. The participants will be provided with capsules sufficient for at least 3 weeks. The second 3-week portion of the capsules will be dispensed at 3-week follow-up visits by a study coordinator. A study coordinator will be given a jar with the study product by an unblinded staff person not-involved in this study. The not-involved staff member will be in possession of the identified randomization list and will provide this list after completing the enrollment and outcome measure analyses. The participants will receive a supplement intake diary to note the taken pills and a study coordinator will count the remaining pills at 3 and 6-week visits.

Data from the exercise interventions will be collected and stored in the study database. Following each session, participants will be asked to provide a rating of perceived exertion (RPE) for the session according to the Borg CR10 scale.

Table 1. Data collection summary by study visit.

Study phase	Pre-randomization		Randomization	
Visit description (FU=follow-up, CO=close-out)	Screen	Baseline	FU	CO
Visit number	1	2	3	4
Week number	-2	0	3 (+ or - 7 days)	6 (+ or - 7 days)
Informed consent, review of inclusion/exclusion criteria	X			
Medical history and medications, MSSE	X			
Height	X			
Weight	X	X	X	X
BMI (calculated in database only)	X			
Demographics information	X			
Physical Exam/nursing assessment	X*	X*		
Monitor vital signs	X	X	X	X
Ambulatory BP recording	X	X	X	X

CHAMPS Questionnaire	X			
Pregnancy test	X			
6 minute walk test		X		X
Late Life Function & Disability Instrument		X		X
Randomization		X		
Blood collection		X	X	X
Urine collection		X	X	X
Arterial stiffness		X		X
Dispense Supplement Intake Diary		X	X	
Dispense Study Supplement (NR or Placebo)		X	X	
Pill counts, collect diaries, assessment of adverse experiences			X	X
Collection of AEs and update medication changes		X	X	X

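### The supplement exclusion covers only regular NR use, so NMN at entry and any NAD+ precursor bought during the study are allowed and can dilute the NREx–PLEx contrast by an amount the documents do not let one size

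*Combined protocol and SAP*

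**What the plan says.** Section 6.1, Table 3.1.1, contains a single criterion about supplements: "Regular consumption of nicotinamide riboside supplement". It names one compound, does not define regular, and is an entry criterion only.

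Section 4 (Background) describes a class, not one compound: "replenishment of NAD+ levels with metabolites (e.g., nicotinamide riboside (NR) or NMN) may be the key to enhancing vascular function". The animal finding behind the combination with exercise was obtained with the other member of that class: "in old mice with replenished NAD+ by administration of nicotinamide mononucleotide (NMN), exercise was more effective in stimulating SIRT1 activity".

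The checks that might touch on outside products are these:

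- Section 6.3 has staff carry out "a review of their medical history, medication use" at screening, and section 6.11 mentions a medication inventory. Neither names supplements.
- Sections 6.4 and 6.8 state: "We will also collect adverse events and update medication changes". Table 1 ticks this at baseline, week 3 and week 6. No action follows from an answer.
- Section 6.6 concerns the study capsules: "The participants will receive a supplement intake diary to note the taken pills". The pill counts are also of study product.
- Section 10 (Statistical Analysis Plan) names no analysis or listing of outside precursor use.

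For planning, section 6.10 assumes "the mean decrease in SBP after a 6-week of intervention to be 20 mmHg, 10 mmHg and 15 mmHg" in NREx, PLEx and NR respectively, and "the standard deviation of the SBP decreases to be 10", with 15 evaluable participants per group.

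**The concern.** PLEx is meant to show what exercise does without NAD+ replenishment. The sponsor evidently sees the threat, since regular NR users are kept out. But a site applying the criterion exactly as written would admit a daily NMN user or an occasional NR user, and no instruction discourages anyone from buying either product after randomization.

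There are two routes to dilution:

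- **Starting on study.** A PLEx participant who starts a precursor after baseline is, on the protocol's reasoning, moving towards NREx.
- **Use before entry.** A participant already replenished at baseline has less deficit for the study NR to correct, so the response in NREx is blunted.

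Aim 1 (section 5) is to supply the data that will size a full-scale trial. A diluted contrast would be carried into that projection, and with no question about supplements nobody could tell afterwards whether dilution had occurred.

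**Working it through.** **Inputs.** Mean SBP decreases of 20 (NREx), 10 (PLEx) and 15 (NR) mmHg, SD 10, n = 15 per group, all from section 6.10. The documents do not give the frequency of precursor use, a human NMN effect, or the change U in untreated people. Alpha and sidedness for the power figure are not stated either; I take alpha = 0.05.

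**The plan's own figure.** NREx − PLEx = 20 − 10 = 10 mmHg. The normal approximation is power = Φ(δ/(σ√(2/n)) − z), with δ/(σ√(2/n)) = 10/(10 × √(2/15)) = 2.739.

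- One-sided: Φ(2.739 − 1.645) = 86.3%; t test 84.8%.
- Two-sided: Φ(2.739 − 1.960) = 78.2%; t test 75.3%.

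The stated 85% is matched by a one-sided test, so 10 mmHg is the contrast to work from.

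**Route 1: starting a precursor after baseline, in PLEx.** Let s be the degree of substitution for study NR (1 = full). A starter's expected decrease is 10 + 10s instead of 10, so k starters among 15 reduce the contrast by 10 × s × k/15.

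- s = 1: 10/15 = 0.67 mmHg per starter, leaving 9.33.
- s = 0.5: 0.33 mmHg per starter.

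This is an upper-end figure, because it credits the starter with the full 6-week effect. With one full-substitution starter and SD held at 10, power by t test moves from 84.8% to 80.2% one-sided, or from 75.3% to 69.4% two-sided. Required n scales with 1/δ², so a projection from 9.33 instead of 10 would be larger by (10/9.33)² − 1 ≈ 15%. A starter in NREx already receives NR and is assumed to gain nothing more.

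**Route 2: stable use before baseline.** Section 10 analyses differences from baseline, so a stable user's replenishment effect on SBP is already in the baseline. On section 6.10's figures, exercise added to replenishment is worth 20 − 15 = 5 mmHg. With full substitution a stable user therefore shows U + 5 in either exercise arm. Taking U = 0 for illustration:

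| Stable users (of 15 per arm) | NREx mean | PLEx mean | Contrast |
|---|---|---|---|
| none | 20.00 | 10.00 | 10.00 |
| one, in PLEx only | 20.00 | 10 − 5/15 = 9.67 | 10.33 |
| one, in NREx only | 20 − 15/15 = 19.00 | 10.00 | 9.00 |
| one in each | 19.00 | 9.67 | 9.33 |

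A stable user in PLEx alone would slightly widen the contrast on these figures. For such a user to show the NREx decrease of 20, U would have to be 15. NR alone would then do nothing (15 − 15 = 0) and exercise alone would do harm (10 − 15 = −5), which contradicts the trial's premise.

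If a share p of both arms are stable users with a common response r, then

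contrast = [20(1 − p) + rp] − [10(1 − p) + rp] = 10(1 − p),

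whatever r is. At U = 0, NREx falls by 15p and PLEx by 5p, so the loss comes mainly through NREx. For example, p = 0.05 gives 9.5 mmHg and p = 0.10 gives 9.0 mmHg. No value of p is documented, and p = 0 is possible.

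**The case against.** The strongest reply has four parts.

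1. **Size.** Use may be rare, and it cannot be assumed both common enough to cost much of the effect and rare enough to exclude at almost no cost. This stands: the low end of the loss is zero.
2. **Precision.** The pilot's 95% confidence interval for NREx − PLEx has a half-width of about 2.048 × 10 × √(2/15) = 7.5 mmHg. One starter moves the estimate by at most 0.67 mmHg, about 9% of that. This stands too, and limits the priority of the point.
3. **Randomization and blinding.** Use at entry is balanced in expectation, so this is not confounding. That is correct, but balance does not prevent dilution: equal shares in both arms still give 10(1 − p).
4. **Existing checks.** The medication review may pick up some use, and the consent pages, which are not available here, may instruct participants about supplements. Both are possible. In the available text, though, supplements are not named in that review and no answer leads to any action.

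A reader might also infer that the protocol treats NMN as equivalent to NR. It does not: section 4 gives both as examples of one class, claims no equal potency, and rests the NMN–exercise evidence on mice. Full substitution is therefore an assumption of the calculation above.

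**Conclusion.** The gap in the wording is clear. The exclusion is narrower than the protocol's own rationale, and no visible provision bars, acts on or reports NMN at entry or any non-study NR or NMN product during the 6 weeks. The expected direction, on that rationale, is dilution of the NREx–PLEx contrast.

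The size is not established. About 0.67 mmHg per participant applies only to a PLEx participant of 15 who starts a precursor after baseline and obtains the full effect. For stable pre-study users the expected contrast is about 10(1 − p), assuming the same share p in both arms and full substitution. It would be tempting to conclude that every NMN user in PLEx costs 0.67 mmHg, or that a specific percentage of the effect is lost. The documents support neither: the first ignores the change-from-baseline analysis, and the second needs a frequency of use that is not given. This is a worthwhile low-cost improvement, not a threat to the trial's validity.

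**What to change.** - **Section 6.1, Table 3.1.1:** replace the criterion with current use of NR or NMN supplements. If other NAD+ precursors are to be covered, give them as a named product list, so that staff need not judge why a participant takes something.
- **Section 6.6:** add that participants in all three arms are asked not to start any such non-study product until after the week-6 recording.
- **Sections 6.4 and 6.8, Table 1:** ask about these products within the medication update already scheduled at baseline, week 3 and week 6.
- **Section 10:** report the number of users by arm.

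The cost is one eligibility line, one instruction, one question at existing visits and one row in a table, with no new visit or procedure. The downside is losing the few volunteers who take these products.
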